7.5.4 Physical Function as Measured by NSAA

For the purposes of calculating total NSAA score, classification of missing data should be applied as follows:

Class 1 - Either of the following:

- ‘Was assessment attempted?’ = ‘No’ and the reason given is ‘Declined to perform test’ or ‘Other’. In this case, each item score will be imputed using the mode of the non-missing scores for the same item and visit across all subjects randomised to the same treatment and in the same concomitant steroid stratum and Group (i.e. Group A, target population or Group B, off-target population). If there are multiple mode values then the lowest modal value will be used. The total score will be re-derived as the sum of the 17 imputed item scores.
- ‘Was assessment attempted?’ = ‘Yes’ but one or more of the item scores is missing. In this case one of two possible methods will be followed:

- If ≥ 9 out of 17 items have been completed with ≤ 8 missing, then the missing item scores for that subject at that visit will be imputed using the mode of the non-missing item scores for the subject and visit. If there are multiple mode values then the lowest modal value will be used. The total score will be re-derived as the sum of the 17 non-missing and imputed item scores.
- If ≤ 8 out of 17 items have been completed with ≥ 9 missing, then the missing item scores for that subject at that visit will be imputed as zero. The total score will be re-derived as the sum of the 17 non-missing and imputed item scores.

Class 2 - 'Was assessment attempted?' = 'No' and the reason given is 'Unable to physically perform the test'. In this case all item scores and the total score will be imputed to zero.

For the purposes of calculating cumulative number of failed items, NSAA data will first be classified and imputed according to the above rules and the assessment of item failure will then be determined using the values after imputation.

7.5.5 Muscle Strength Evaluated by Knee Extension and Elbow Flexion as Measured by Hand-held Myometry

Class 1 – Either of the following:

- 'Was assessment attempted?' = 'No' and the reason given is 'Declined to perform test' or 'Other'.
- 'Were all 4 elements of the extension/flexion assessment attempted?' = 'No' and the reason given is 'Declined to perform test' or 'Other'. Any missing elements of the test (left/right knee extension or left/right elbow flexion) will be classified as 1.

Class 2 – Either of the following:

- 'Was assessment attempted?' = 'No' and the reason given is 'Unable to physically perform the test'.
- 'Were all 4 elements of the extension/flexion assessment attempted?' = 'No' and the reason given is 'Unable to physically perform the test'. Any missing elements of the test (left/right knee extension or left/right elbow flexion) will be classified as 2.

7.5.6 Fat Fraction of Vastus Lateralis Muscles as assessed by MRS

All missing data for this endpoint will be Class 1.

7.5.7 Time to Run/Walk 10 Metres

Class 1 – 'Was assessment performed?' = 'No'.

Class 2 – 'Was assessment performed?' = 'Yes' but 'Was assessment completed?' = 'No' and 'Distance' is missing and 'Duration walked' is missing and '10-Metre Walk/Run test Grading' response is '1 = Unable to walk independently' or '2 = Unable to walk independently, but can walk with full leg calipers (KAFOs) or with support from a person'. Note that if the grading is >2 but the 'Duration walked' is genuinely missing, this should be treated as Class 1 missing data.

7.5.8 Paediatric Outcomes Data Collection Instrument (PODCI) Scores

All missing data for this endpoint will be Class 1.

7.5.9 Percent Predicted 6MWT

Missing values for the 6MWT will be classified and imputed as described above for that endpoint, prior to finding the percent predicted 6MWT values.

7.5.10 Fat Fraction and Cross-Sectional Area of 5 Thigh Muscles as Assessed by MRI

All missing data for this endpoint will be Class 1.

7.5.11 Time to 10% Persistent Worsening in 6MWT

Missing values for the 6MWT will be classified and imputed as described above for that endpoint, prior to finding the time to 10% persistent worsening in 6MWT. Note that any imputed 6MWT values post early withdrawal will also be considered for the purposes of the time to event analysis.

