4.3.5 Time to 10% Persistent Worsening in 6MWT

Time to 10% persistent worsening in 6MWT will be defined as the time from the date of first study treatment to the last time the 6MWT was not $\geq 10\%$ worse than the baseline 6MWT (McDonald, et al., 2013). If a subject has not achieved $\geq 10\%$ persistent worsening in 6MWT, then time to 10% persistent worsening in 6MWT will be censored at the date of the last 6MWT assessment (including imputed assessments per Section 4.4.4.1), i.e. the 18 month assessment.

The number and percentage of subjects who achieved $\geq 10\%$ persistent worsening in 6MWT and of those censored will be summarised by treatment group. The Kaplan-

Meier estimates of the median, 25th percentile and 75th percentile for time to $\geq 10\%$ persistent worsening in 6MWT, together with the associated 2-sided 95% confidence intervals (CI) will also be presented by treatment group. Time to 10% persistent worsening in 6MWT will also be presented graphically by treatment group using a Kaplan-Meier plot.

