4.4.4 Handling of Missing Data

4.4.4.1 Classification and Imputation

For the efficacy analyses, any missing data for continuous values for a subject will be classified as follows:

1. the subject has missing data due to reasons other than being non-ambulatory or physically unable to perform the test / assessment
2. the subject has missing data due to being either non-ambulatory or otherwise physically unable to perform the test / assessment.

Any missing values classified as 1 will be imputed using the mean of all non-missing values for the respective measurement and timepoint across all subjects randomised to the respective treatment and in the respective concomitant steroid stratum and Group (i.e. Group A, target population or Group B, off-target population).

Any missing values classified as 2 will be imputed by setting the value to zero or to twice the maximum non-missing value recorded across all subjects depending on the directionality of the test.

In all cases, imputation of any data classified as 1 will be completed first, followed by imputation of any data classified as 2.

Classification and imputation of missing data will be completed prior to any transformation of the data for analysis. For example transformation of the timed function test results for presentation of velocity or any log transformation applied as needed (per Section 4.4.2).

For binary or time to event variables where missing data means that the binary response or time to event cannot be determined, the missing data from which the variable is derived (e.g. 6MWT values) will first be classified and imputed, as described above, in order to then derive the binary response or the time to event. Exceptions to this are where the criteria for deriving the binary response themselves refer to presence of missing data, for example loss of ambulation. The classification described above will be used for the relevant missing data in these cases in order to confirm physical inability to complete the respective test. Further details are given below regarding the rules for derivation of the binary endpoints in the presence of missing data.

For the NSAA assessment, where the total score is a sum of ordinal item scores, imputation of Class 1 and Class 2 data will follow a different approach as defined in Appendix 7.5.4.

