The rules for classifying missing data from the responses on the eCRF and any additional considerations for imputation are given in Appendix 7.5 for each respective endpoint. Unless otherwise stated, only the value of interest for analysis will be classified and imputed. For example, the 'duration' for the 4SC assessment will be imputed but not the 4-stair ascent grading.

Note that missing data at any scheduled timepoint should be imputed according to the above rules. This includes any scheduled timepoints after a subject withdraws early. In these cases, where the final assessment prior to withdrawal was missing and determined to be Class 2 missing data, all missing assessments post withdrawal will also be considered Class 2. Otherwise, these will be considered Class 1. Note that where this applies to an NSAA assessment, 'Class 1' will refer to the scenario where

'Was assessment attempted?' = 'No'. Where a date of assessment is required, the predicted date for imputed timepoints post withdrawal will be used. The same approach will be followed for any completely missing visits prior to withdrawal or completing the study, where no information has been entered into the respective CRF assessment page indicating whether or not it was performed.

Where data entered into the CRF for an assessment are ambiguous such that they do not reflect any of the expected responses outlined in Appendix 7.5 and therefore missing data cannot be classified, a worst case approach will be followed and the missing data will be assumed Class 2.

A review will be performed at the BDRM to confirm correct classification of missing data. This may identify data entered into the CRF assessment page which comply with Appendix 7.5 but additional information is available to contradict the classification (for example in comments). Any such cases will be assessed on a case by case basis to determine the appropriate classification to be applied.

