7.5.13 Time to Persistent Loss of Standing (Baseline Through End of Study)

The following rules will be applied in order to identify subjects who meet the criteria specified in Section 4.3.7 for persistent loss of standing. Note that any imputed values post early withdrawal will also be considered for the purposes of the time to event analysis:

- Classification and imputation of the NSAA data will be applied as described above. Where Class 2 missing data are identified, the score for the 'Rise from floor' item on the NSAA assessment will be assumed to be '0b - Unable' for the purposes of determining loss of standing. Where Class 1 missing data are identified, the score for the 'Rise from floor' item will be carried forward from the last non-missing score for this item for the subject. If the Class 1 missing data are from a baseline assessment, the score for this item will be assumed >0 .
- Classification and imputation of the Time to Rise from Floor data will be applied as described above. Where there are Class 1 missing data for the Rise from Floor assessment and therefore the 'Rising from floor grading' is missing, the grade will be carried forward from the last non-missing Rising from floor grading for the subject. If the Class 1 missing data are from a baseline assessment, the Rising from floor grading will be assumed >1 .

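### Time to 10% persistent worsening in 6MWT: for a boy who withdraws with Class 1 missing data, event status is set by his baseline against a cell mean, whatever was observed

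*SAP*

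**What the plan says.** SAP 4.3.5 measures the time from first study treatment to the last visit at which 6MWT was not yet at least 10% below baseline. The time of a boy without persistent worsening "will be censored at the date of the last 6MWT assessment (including imputed assessments per Section 4.4.4.1), i.e. the 18 month assessment". SAP 7.5.11 adds that "any imputed 6MWT values post early withdrawal will also be considered for the purposes of the time to event analysis".

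The imputed values come from SAP 4.4.4.1:

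- **Which visits.** Every missing scheduled visit is imputed: "This includes any scheduled timepoints after a subject withdraws early". Imputed visits carry their predicted dates.
- **Which class.** If the final assessment before withdrawal was itself missing as Class 2 (physical inability), "all missing assessments post withdrawal will also be considered Class 2. Otherwise, these will be considered Class 1".
- **Class 1 value.** It is "imputed using the mean of all non-missing values for the respective measurement and timepoint across all subjects randomised to the respective treatment", within the same steroid stratum and Group.
- **Class 2 value.** "Any missing values classified as 2 will be imputed by setting the value to zero or to twice the maximum non-missing value". For 6MWT, where lower is worse, SAP 4.4.4.2 makes this 0 m.
- **Order.** "imputation of any data classified as 1 will be completed first, followed by imputation of any data classified as 2". The Class 1 means therefore contain no Class 2 zeros.

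SAP 2.8 keeps the early withdrawal visit separate from the end-of-study visit, so a withdrawn boy's month-18 value is always imputed. The binary version of the endpoint (SAP 4.3.6 and 7.5.12) uses the same imputed 6MWT values. For time to persistent loss of standing, SAP 7.5.13 likewise says that "any imputed values post early withdrawal will also be considered for the purposes of the time to event analysis".

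**The concern.** Kaplan-Meier and Cox methods deal with incomplete follow-up by censoring. Here a boy who leaves is instead completed to month 18 with a group average, and the completed record is analysed as if observed. An average says nothing about whether this boy fell by 10% from his own baseline, yet it settles the question.

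Three things are at stake:

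- Worsening that was seen can disappear, and worsening that was never seen can appear.
- The mean is specific to the arm, so any difference between arms feeds back into the hazard ratio through the withdrawn boys.
- Events and follow-up time that were imputed once carry the same weight as observed ones, so the confidence interval does not reflect that they are unknown.

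**Working it through.** The documents give no event count, hazard ratio or power for this endpoint, so there is no planned figure to reproduce. They also give no 6MWT distribution. Every 6MWT value below is an assumption made for illustration.

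**The rule.** Let B be a boy's baseline and m18 the month-18 mean of his arm, steroid stratum and Group. Worsening at a visit means a value of at most 0.9 × B, and it must still be present at month 18. For a Class 1 withdrawal the month-18 value is m18, so he is an event if and only if m18 ≤ 0.9 × B, that is B ≥ m18/0.9. His own post-baseline values can move the event date but not the event status. A Class 2 withdrawal has 0 m, which is always at most 0.9 × B, so he is always an event.

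**Two boys.** Assume cell means at months 3 to 18 of 398, 394, 388, 380, 370 and 360 m. The cut is 360/0.9 = 400 m. Both boys leave after month 6.

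- Boy A has baseline 430 m and observed values 428 and 432 m. His threshold is 0.9 × 430 = 387 m. The imputed 388 m at month 9 is above it; 380, 370 and 360 m are below it. The SAP makes him an event dated month 9. On observed data he is stable and censored at month 6.
- Boy B has baseline 390 m and observed values 345 and 330 m, which are 45/390 = 11.5% and 60/390 = 15.4% worse. His threshold is 0.9 × 390 = 351 m. The imputed 388, 380, 370 and 360 m are all above it. The SAP makes him event-free to month 18. On observed data he had worsened and had not recovered when he left.

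**Dependence on arm.** Assume m18 = 370 m in one arm and 350 m in the other. A withdrawn boy with baseline 400 m has a threshold of 360 m. He is a non-event in the first arm (370 > 360) and an event in the second (350 ≤ 360), with the same history.

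**Scale.** SAP 2.5 gives 8% drop-out and 110 boys in the target population: 0.08 × 110 = 8.8, about 9. If all 9 left at month 3, imputed follow-up would be 9 × 15/(110 × 18) = 6.8% of planned boy-months. If all left at month 15 it would be 9 × 3/(110 × 18) = 1.4%.

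**Misclassification under assumed values.** A simulation used 4,000 trials per scenario and cells of 25 boys with 2 withdrawn. It assumed mean baseline 400 m (SD 40 to 80), mean 18-month decline 20 to 60 m (SD 60) and measurement SD 15 m. The status assigned under the SAP was compared with the status the boy's own month-18 value would have given.

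| Withdrawal | Event created | Event erased | True share of events | Share under the SAP |
|---|---|---|---|---|
| Random | 19–27% | 20–27% | 37–63% | 31–69% |
| Faster decliners leave | 2–7% | 35–62% | 85–97% | 27–63% |

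Percentages are of withdrawn Class 1 boys. Under random withdrawal 45–54% are misclassified, but errors in the two directions largely offset. When faster decliners leave, the net effect is to lose events.

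**The case against.** The strongest reply is one of weight. SAP 4.3 labels these endpoints supportive, with nominal p-values. About 9 boys are expected to withdraw, and some will be Class 2. No primary or key secondary conclusion rests on this analysis. That stands and sets the severity.

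A second reply concerns timing. The SAP is final, and the addendum describes changes made after database lock. Replacing the derivation now would be post hoc. That also stands, and it favours an added analysis over a substitution.

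A reader might draw four stronger conclusions that the documents do not support:

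- **That both time-to-event endpoints share the fault.** Loss of standing uses no arm mean. The boy's last rise-from-floor grading is carried forward. Under the addendum (Change 4) the NSAA item takes the SAP 7.5.4 value, a cell mode when the test was not attempted, and a Class 1 zero is read as 0a. An event needs 0b together with grade 1, so a Class 1 NSAA imputation cannot create one. Only the run to month 18 on imputed visits is common to both endpoints.
- **That baseline decides for every withdrawn boy.** It does so for Class 1 only.
- **That the share of withdrawn boys above the cut measures error.** With an assumed baseline of 400 m (SD 60), the share labelled events at m18 = 380, 360 or 340 m is 36%, 50% or 64%. If change has SD 60 m and is independent of baseline, the true share is about 37%, 50% and 63%. The totals agree; it is the individual boys who are misclassified.
- **That worsening first seen at month 18 needs confirmation at a second visit.** SAP 4.3.6 expressly admits worsening at the end of the study. Requiring two consecutive visits would be a different endpoint, on which statisticians may differ.

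**Conclusion.** The point holds for time to 10% persistent worsening in 6MWT and Class 1 withdrawals. That part is a matter of logic: it follows from SAP 2.8, 4.3.5, 4.4.4.1 and 7.5.11 read together and needs no assumed value. The rule can reverse what was observed in an individual boy, it depends on his arm, and it counts imputed follow-up as observed.

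The size of the effect on the hazard ratio is not established. The misclassification rates rest on assumed 6MWT distributions and withdrawal patterns. The one directional indication is that events are lost if faster decliners leave; leaving Class 2 zeros out of the cell means also favours erasing events. With about 9 of 110 boys affected and an exploratory endpoint, the severity is minor.

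**What to change.** In SAP 4.3.5 and 7.5.11:

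1. Use no Class 1 imputed 6MWT value after withdrawal.
2. Count as an event any worsening of at least 10% that persists through the boy's last observed assessment, including the early withdrawal visit.
3. Keep physical inability (Class 2) as an event, as now.
4. Otherwise censor at the last observed assessment.

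Align the binary endpoint in 4.3.6 and 7.5.12 so that one boy cannot be censored in one analysis and an event in the other. State there how a withdrawn boy without observed worsening is handled. For loss of standing (4.3.7 and 7.5.13), censor at the last observed assessment.

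If the pre-specified analysis must stand, report this version beside it and label it as added.

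The cost is SAP wording and derivation code, somewhat less follow-up time, and reliance on non-informative censoring. That last assumption is also doubtful if faster decliners leave, although a boy whose worsening was seen before he left would then be counted as an event.

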7.5.12 Proportion of Subjects with $\geq 10\%$ Persistent Worsening in 6MWT

Missing values for the 6MWT will be classified and imputed as described above for that endpoint prior to finding the proportion of subjects with $\geq 10\%$ persistent worsening in 6MWT.

7.5.13 Time to Persistent Loss of Standing (Baseline Through End of Study)

The following rules will be applied in order to identify subjects who meet the criteria specified in Section 4.3.7 for persistent loss of standing. Note that any imputed values post early withdrawal will also be considered for the purposes of the time to event analysis:

- Classification and imputation of the NSAA data will be applied as described above. Where Class 2 missing data are identified, the score for the 'Rise from floor' item on the NSAA assessment will be assumed to be '0b - Unable' for the purposes of determining loss of standing. Where Class 1 missing data are identified, the score for the 'Rise from floor' item will be carried forward from the last non-missing score for this item for the subject. If the Class 1 missing data are from a baseline assessment, the score for this item will be assumed >0 .
- Classification and imputation of the Time to Rise from Floor data will be applied as described above. Where there are Class 1 missing data for the Rise from Floor assessment and therefore the 'Rising from floor grading' is missing, the grade will be carried forward from the last non-missing Rising from floor grading for the subject. If the Class 1 missing data are from a baseline assessment, the Rising from floor grading will be assumed >1 .

7.5.14 Proportion of Subjects Who Lose Ambulation

The following steps will be completed in order to identify subjects who meet the criteria specified in Section 4.3.8 for loss of ambulation:

- Missing 6MWT values will be classified in order to identify any Class 2 missing values, i.e. where the subject meets the criterion for being unable to perform the 6MWT due to physical inability.

- Any missing 10-metre walk/run test values will be classified and imputed. The imputed values will be used to identify subjects who meet the criteria for being unable to complete the 10-metre walk/run test in 30 seconds or less without any support or devices. Where Class 1 missing data are identified and the imputed duration walked is ≤ 30 seconds, the '10-Metre Walk/Run test Grading' will be carried forward from the last non-missing grading for the subject in order to determine whether the subject was able to complete the test without any support or devices. If the Class 1 missing data are from a baseline assessment, the 10-Metre Walk/Run test Grading will be assumed >2 for the purposes of determining loss of ambulation (i.e. able to complete the test without support or devices).

7.5.15 Type of DMD Mutation, LTBP4 and Osteopontin Genotype

No imputation will be applied to this data. Any missing values for these assessments will be excluded from summaries and analyses as applicable. Where a subject has a missing value such that they cannot be assigned to a group for evaluation of subgroups, they will be excluded from the respective subgroup summaries and analyses.

7.5.16 DMD Serum Biomarker

No imputation will be applied to this data. Any missing values for this assessment will be excluded from summaries and analyses as applicable.

7.6 Outputs to be Reviewed at the Safety Review Meetings

The following tables, figures and listings will be reviewed by the IDMC at the 3 monthly safety review meetings. The IDMC will meet every 3 months from the first subject randomised. All tables and listings provided to the IDMC at safety reviews will be presented for the overall subject population.

Table 14.1.1.1.1.1 Subject Disposition

Table 14.1.1.1.2.1 Disposition of Screened Subjects

Listing 16.2.1.1 Subject Completions and Withdrawals

Listing 16.2.2.1 Eligibility - Inclusion and Exclusion Criteria

Listing 16.2.3.1 Analysis Sets

Table 14.1.1.2.1 Major Protocol Deviations

Listing 16.2.3.2 Protocol Deviations

Table 14.1.2.1 Demography

Listing 16.2.4.1 Demography

Table 14.1.3.1 Medical History

Listing 16.2.4.2 Medical History

Table 14.1.3.2 DMD Diagnosis

Listing 16.2.4.3 DMD Diagnosis

Table 14.1.4.1 Administration of Study Treatment

Table 14.1.4.2 Modifications of Study Treatment

Table 14.1.4.3 Duration of Modifications of Study Treatment

Listing 16.2.5.1 Investigational Product Dispensing

Listing 16.2.5.2 Investigational Product Modifications

Table 14.1.5 Ankle Range of Motion

Listing 16.2.5.3 Ankle Range of Motion

Table 14.1.6 Muscle Strength Test Modified MRC Grade

Listing 16.2.5.4 Muscle Strength Test Modified MRC Grade

Table 14.3.1.1.1 Summary of Treatment-Emergent Adverse Events

Table 14.3.1.2.1 Summary of Treatment-Emergent Adverse Events by MedDRA System Organ Class and Preferred Term

Table 14.3.1.3.1 Summary of Serious Treatment-Emergent Adverse Events by MedDRA System Organ Class and Preferred Term

Table 14.3.1.4.1 Summary of Treatment-Emergent Adverse Events Leading to Withdrawal by MedDRA System Organ Class and Preferred Term

Table 14.3.1.6.1 Summary of Treatment-Emergent Adverse Events Leading to Death by MedDRA System Organ Class and Preferred Term

Table 14.3.1.7.1 Summary of Treatment-Emergent Adverse Events Leading to Discontinuation of IMP by MedDRA System Organ Class and Preferred Term

Table 14.3.1.8.1 Summary of Treatment-Emergent Adverse Events by MedDRA System Organ Class, Preferred Term and Severity

Table 14.3.1.9.1 Summary of Treatment-Emergent Adverse Events by MedDRA System Organ Class, Preferred Term and Relationship to Study Treatment

Table 14.3.1.11.1 Treatment-Emergent Bronchopulmonary Adverse Events (BAEs)

Listing 16.2.7.1 Adverse Events

Listing 16.2.7.2 Serious Adverse Events

Listing 16.2.7.3 Adverse Events Leading to Discontinuation of IMP

Listing 16.2.7.4 Adverse Events Leading to Dose Reduction or Discontinuation of IMP

Table 14.3.2.1 Haematology Values and Change from Baseline over Time

Table 14.3.2.2 Haematology Values and Change from Baseline over Time

Table 14.3.2.3 Platelets Count Values over Time

Figure 14.2.7.1 Plot of Mean Platelets Count by Treatment over Time

Table 14.3.2.4 Shift in Haematology Values over Time

Figure 14.2.7.2.1 Box and Whisker Plot of Selected Haematology Results by Treatment over Time

Figure 14.2.7.2.2 Patient Plots of Selected Haematology Results over Time*

Listing 16.2.8.1 All Haematology Values

Table 14.3.3.1 Clinical Chemistry Values and Change from Baseline over Time

Table 14.3.3.2 Shift in Clinical Chemistry Values over Time

Figure 14.2.7.3.1 Box and Whisker Plot of Selected Clinical Chemistry Results by Treatment over Time

Figure 14.2.7.3.2 Patient Plots of Selected Clinical Chemistry Results over Time*

Listing 16.2.8.2 All Clinical Chemistry Values

Table 14.3.4.1 Coagulation Values and Change from Baseline over Time

Listing 16.2.8.4 All Coagulation Values

Listing 16.2.8.6 All Liver Function Values

Table 14.3.5 Summary of Vital Signs and Change from Baseline over Time

Listing 16.2.9.1 Vital Signs

Table 14.3.6.1 Summary of ECG Results and Change from Baseline over Time

Table 14.3.6.2 Shift in ECG Interpretation

Table 14.3.6.3 Incidence of Outliers in ECG Results

Figure 14.2.8 Plot of Mean QTcF Values by Treatment over Time

Listing 16.2.9.3 ECG Results

Table 14.3.7 ECHO Values and Change from Baseline over Time

Listing 16.2.9.4 All Echocardiography (ECHO) Values

Table 14.3.8.1 Pulmonary Function Test and Change from Baseline over Time

Table 14.3.8.2 Percent Predicted Values for Pulmonary Function Test and Change from Baseline over Time

Figure 14.2.9.1 Plot of Mean Peak Expiratory Flow (L/min) Values by Treatment over Time

Figure 14.2.9.2 Plot of Mean Forced Vital Capacity (L) Values by Treatment over Time

Figure 14.2.9.3 Plot of Mean % Predicted Peak Expiratory Flow (%) Values by Treatment over Time

Figure 14.2.9.4 Plot of Mean % Predicted Forced Vital Capacity (%) Values by Treatment over Time

Listing 16.2.9.5 All Pulmonary Function Test Values

Table 14.3.9.1.2 Concomitant Medications

Table 14.3.9.2.2 Concomitant Steroid Treatments

Listing 16.2.9.6.1 Prior and Concomitant Medications

Listing 16.2.9.6.2 Prior and Concomitant Steroid Treatments

Excel listings of selected laboratory parameter results by visit for each subject in the all enrolled subjects analysis set. This will include the dose administered at each visit alongside the results.*

Excel listing of site level deviations.

* *Output is only to be produced for safety reviews and not as part of the final analysis.*

In addition to the above list, the following repeat tables presented by country will also be provided once 30 subjects have been randomised:

Table 14.1.1.1.1.2 Subject Disposition by Country

Table 14.1.1.1.2.2 Disposition of Screened Subjects by Country

Table 14.1.1.2.2 Major Protocol Deviations by Country

Table 14.1.2.2 Demography by Country

Table 14.3.1.1.2 Summary of Treatment-Emergent Adverse Events by Country

Table 14.3.1.2.2 Summary of Treatment-Emergent Adverse Events by Country, MedDRA System Organ Class and Preferred Term

Table 14.3.1.3.2 Summary of Serious Treatment-Emergent Adverse Events by Country, MedDRA System Organ Class and Preferred Term

Table 14.3.1.4.2 Summary of Treatment-Emergent Adverse Events Leading to Withdrawal by Country, MedDRA System Organ Class and Preferred Term

Table 14.3.1.6.2 Summary of Treatment-Emergent Adverse Events Leading to Death by Country, MedDRA System Organ Class and Preferred Term

Table 14.3.1.7.2 Summary of Treatment-Emergent Adverse Events Leading to Discontinuation of IMP by Country, MedDRA System Organ Class and Preferred Term

Table 14.3.1.8.2 Summary of Treatment-Emergent Adverse Events by Country, MedDRA System Organ Class, Preferred Term and Severity

Table 14.3.1.9.2 Summary of Treatment-Emergent Adverse Events by Country, MedDRA System Organ Class, Preferred Term and Relationship to Study Treatment

Table 14.3.1.11.2 Treatment-Emergent Bronchopulmonary Adverse Events (BAEs) by Country

The following additional tables will also be provided once at least 50 subjects have been randomised and have completed at least one month of treatment:

Table 14.3.1.10.1 Summary of Treatment-Emergent Adverse Events by Steroid Type at Baseline, MedDRA System Organ Class and Preferred Term

Table 14.3.1.10.2 Summary of Treatment-Emergent Adverse Events by Country, Steroid Type at Baseline, MedDRA System Organ Class and Preferred Term

For the purposes of IDMC safety reviews, the summaries relating to antibiotic use will be excluded from the above two tables as this is not relevant to safety. These summaries will only be included for the final analysis (and interim analyses if required).

The summary tables listed above will be repeated using the blinded (dummy) randomisation so that the blind is maintained, and these outputs will be sent to

Italfarmaco at each safety review. Italfarmaco will not receive any figures or listings for the safety reviews.

At each safety review, individual outputs will be compiled into a single pdf file for tables, figures and listings respectively with hyperlinks applied to navigate to each output. The compiled files will be provided alongside the individual output files.

